Purpose: The purpose of this study is to translate neuroscience on emotion, music, and cognition into application for rehabilitation of aphasia, and test the effectiveness and efficiency of a new treatment, using listening to music with lyrics, combined with silent reading of the lyrics, to evoke emotion, engage the amygdala-extrastriate cortical projections, and increase arousal and attention to the reading material, to promote recovery of reading and retention of phrase-level reading material in patients with aphasia.

Significance: The impact of this study is anticipated to be a demonstration of increased effectiveness and efficiency of therapy directed toward recovery of language including reading comprehension in participants with aphasia. In addition, new material will be developed to increase options for treatment. Further, it will provide behavioral evidence to support hypotheses of either independent or shared neural pathways for processing musical and linguistic semantic meaning.

3. **Objectives:** State the research hypothesis or the question that the research will answer. List the research objectives and expected outcomes. **A primary outcome or objective must be identified.** After the statement of the primary objective, secondary objectives may be listed. Objectives should be simple and specific.

Primary objective: test the effectiveness and efficiency of a new treatment, using listening to music with lyrics, combined with silent reading of the lyrics, to promote recovery of reading and retention of phrase-level reading material in participants with aphasia.

Research questions:

1. Is music with lyrics (songs) presented simultaneously with written lyrics effective for facilitating recovery of reading of phrase-level material for participants with aphasia (independent processing)?
2. Is music with lyrics followed by presentation of the written lyrics effective for facilitating recovery of reading of phrase-level material for participants with aphasia (shared processing)?
3. Which procedure, simultaneous presentation or priming with the music/lyrics, is more effective for facilitating recovery of reading of phrase-level material for participants with aphasia?
4. Is one method more efficient for facilitating recovery of reading of phrase-level material for participants with aphasia?
5. Does one procedure result in greater retention of the trained material?

Research Hypotheses:

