Seventh Step--Intervention phase (B) (see flowchart attached), each song (music with lyrics) from set 1 (B1 songs #1-10) will be played in its entirety. When the targeted verse or chorus plays, the written lyrics will be simultaneously shown along with the song lyrics. The ST will point to the words of the targeted verse/chorus which will be silently observed by the participant as they are sung. This will be repeated for all 10 songs. The phrase completion task will then be presented, including the ten phrases from the songs played that day and the five control phrases, without music. The participant will silently or orally read the phrase and orally read and/or circle or point to the phrase completion choice. Correct responses will be verbally reinforced. The next session, each song (music with lyrics) from set 2 (B2 songs #11-20) will be played in its entirety. After the song plays, the written lyrics from the targeted verse or chorus will be presented. The ST will point to the words of the targeted verse/chorus which will be silently observed by the participant. This will be repeated for all 10 songs. The phrase completion task will then be presented, including the ten phrases played that day and the five control phrases. The participant will silently or orally read the phrase and orally read and/or circle or point to the phrase completion choice. Correct responses will be verbally reinforced. This will be repeated for all 10 songs. For all interventions, the number of correct responses will be tallied on a LaPoint Base 10 form and the percent correct will be entered on the graph for that day. The same procedures will be repeated, alternating procedures on sets 1 and 2 on subsequent treatment visits, until a criterion of 9/10 (90%) x 3 consecutive visits is reached on both sets. If the criterion is not reached on one of the intervention sets, defined as no increase in percentage correct x 3 consecutive visits, a correction procedure will be applied using modeling of the correct response. If the criterion still is not reached, that intervention will be determined to be limited in effectiveness and discontinued. Every third session will be videotaped for a reliability check by the recruiter/research team member. When both of the sets (B1 and B2) have been acquired or one acquired and the other discontinued, the number of sessions to criterion will be counted for each intervention. (Expect length of time 2- 12 weeks)

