Eighth Step--Posttest BDAE-3 full version Reading subtests (extended posttest). (Expected length of time one visit)

Ninth Step--Retest retention of 30 phrases 3-week follow-up. (Expected length of time one visit)

Total number of visits: 16-48; total length of time 10-20 weeks per patient.

For CFMH or Roanoke Day Rehab, the PI, who is also the treating SLP, will make clear to subjects each time when standard therapy has ended and a research study intervention is about to begin. The subjects will be told approximately how long the research intervention is expected to take. For CRMH Inpatients, research will be separated in time and completed by a different SLP (the PI).

7. **Data Collection:** Attach a copy of your data collection tool or spreadsheet listing exactly what data is to be gathered during this research study. Describe below the data collection methods and how data be compiled for assessment.

Outcome Measures and Time Points

Pretest/post-test information on the ICF Body Functions/Structures, Activities, and Participation will be provided (Hurkmans et al. 2011).

The Boston Diagnostic Aphasia Examination (BDAE) (Goodglass, Harold, & Kaplan, 1983): Pretest reading scores on the BDAE full version subtests, i.e. B. Word Identification: 1. Word-Picture Match, and 2. Lexical Decision; C. 1. Homophone Matching; D. Derivational and Grammatical Morphology: 1. Matching to spoken sample; E. Oral Reading: 1. Basic oral word reading; F. Oral Reading of Sentences with Comprehension; and G. Reading Comprehension-Sentences and Paragraphs; will be completed prior to baseline A and initiating intervention, and immediately following completion of intervention to assess generalization to non-trained stimuli.

At three weeks follow-up the trained stimuli from all three interventions will be retested to assess retention (see Flow Diagram).

The dependent variables, i.e. differential response to the two interventions (counted as the percent correct responses per day, number of sessions required to achieve mastery at each level (simple counting), retention of the material (number of items remembered).

Reporting Participant Characteristics

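### Once modelling is added to a stalled music set, its later results mix music with modelling, yet the plan counts them for the music procedure without separating them

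*Combined protocol and SAP*

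**What the plan says.** Section 6 (Methodology), Seventh Step, alternates the two music procedures "until a criterion of 9/10 (90%) x 3 consecutive visits is reached on both sets". A stall on one of the music sets is "defined as no increase in percentage correct x 3 consecutive visits". The response is that "a correction procedure will be applied using modeling of the correct response". The only route to a negative verdict comes after that: "If the criterion still is not reached, that intervention will be determined to be limited in effectiveness and discontinued". The phase closes, and the count is taken, under this sentence: "When both of the sets (B1 and B2) have been acquired or one acquired and the other discontinued, the number of sessions to criterion" is then tallied for each intervention.

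Section 7 (Data Collection, Outcome Measures and Time Points) lists three dependent variables: percent correct per day, "number of sessions required to achieve mastery at each level (simple counting"), and items retained. Trained items are retested at three weeks. Section 8 (Statistical Analysis) describes celeration and split-middle lines, the binomial test, the two-standard-deviation band, process control charts, and differences between the control and the two music conditions. Neither section mentions modelling.

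Section 3 (Objectives) sets the questions these data must answer. The first is "Is music with lyrics (songs) presented simultaneously with written lyrics effective for facilitating recovery of reading of phrase-level material", and the second asks the same of priming. Questions 3 to 5 compare the two procedures on effectiveness, efficiency and retention.

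**The concern.** Modelling the correct response on the outcome items is an additional, non-musical component. It is given only to a set that has stalled, and it is described only for the music sets. The other music set may never receive it, and no modelling is described for the control phrases, so the planned comparison with control cannot remove its effect.

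Questions 1 and 2 ask whether each music procedure works. A set that stalled on music and reached criterion after modelling is scored in the same way as one that never stalled. A jump after modelling could also meet a process-control signal rule and be read as an effect of the music. For questions 3 to 5, if one set is corrected and the other is not, the contrast is no longer between two music procedures. If modelling helps, and the weaker procedure is the one corrected, the difference that hypotheses 3 to 5 predict is reduced. With a minimum of four participants, the status of one set can alter the replication finding.

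**Working it through.** The plan gives no effect size, learning rate or error rate for this rule, so there is no figure to reproduce. The check has three parts.

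**1. Tracing the rule (Seventh Step).**
- Path a: no stall, criterion met. Acquired.
- Path b: stall, modelling, criterion met. Not discontinued, because discontinuation requires that the criterion is still unmet. The only other end state is acquired, and the sessions are counted for that music procedure.
- Path c: stall, modelling, criterion not met. Discontinued.

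Paths a and b are recorded identically. Sections 7 and 8 contain no rule that flags, censors or separates sessions after modelling.

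**2. Could path b be luck?** With 10 items at constant accuracy p, P(at least 9 correct) = 10p⁹(1 − p) + p¹⁰. Cubing it gives the chance of meeting the criterion on three given visits.
- p = 0.6: 0.0403 + 0.0060 = 0.0464; cubed, 0.0001
- p = 0.7: 0.1211 + 0.0282 = 0.1493; cubed, 0.0033
- p = 0.8: 0.2684 + 0.1074 = 0.3758; cubed, 0.053

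Over 18 visits there are 16 runs of three, so at p = 0.6 the chance is at most about 16 × 0.0001 = 0.0016. A set stalled near 60% that later meets the criterion has almost certainly learned something after the stall. The calculation cannot say whether music or modelling taught it.

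**3. How often would modelling start?** All inputs here are assumptions except the 10 items and the mastery rule: binomial scores, at most 18 sessions per set, and 20,000 simulated sets per scenario. The stall rule can be read as three visits without a rise (two successive non-rises) or as three successive non-rises. At least one score in the stall must be below 9.

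| True course of the set | Modelling starts before mastery, two non-rises | Three non-rises |
|---|---|---|
| Flat at 40% to 60% | about 99% | about 74% |
| 40% to 95% over 6 sessions | 26% | 2% |
| 40% to 95% over 10 sessions | 66% | 15% |
| 40% to 95% over 15 sessions | 90% | 36% |

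With the modelling effect set to zero, the proportions of rising sets that trigger modelling and still reach criterion on the music curve alone are 26%, 66% and 83% (two non-rises), or 2%, 15% and 33% (three).

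A second illustration (8,000 runs per scenario) shows what the false-acquisition rate depends on. It assumes no music effect, starting accuracy 0.4 to 0.6, learned items 97% correct, the two-non-rise reading, and six visits allowed after modelling. If modelling adds nothing, about 0% of sets are declared acquired. If it adds a learning chance of 0.2 per item per visit, 9% to 23% are. If it adds 0.4, 60% to 74% are. Acquisition before modelling is about 0% throughout.

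**The case against.** The plan never says in words that a set mastered after modelling is acquired. That is an inference, though the two end states leave no alternative. The flowchart cited for this phase is not available and could add a rule, so the finding covers the available text only. The exclusion of the control phrases from correction is also inferred, from the reference to intervention sets; section 7 speaks of three interventions.

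The contrast may be milder than it looks. The therapist already shows the lyrics and points to the words in both procedures, and the form of modelling is not described. Scores are graphed at every session, so a stall stays visible, and the session count includes the stalled visits. In illustrative runs with modelling adding 0.05 to 0.10 accuracy per visit, slower sets still averaged more sessions (11.0 to 14.2) than faster ones (7.7 to 7.9). This limits the damage to the ordering of improving sets; it does not remove the confounding.

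Three stronger readings are tempting, and the documents support none of them.
- A reader might infer that modelling produced the mastery. Nothing says that music stops when modelling starts, so the cause is undetermined.
- A reader might take 99% or 74% as the rate at which a useless procedure is credited with success. Those figures say only how often modelling would start.
- A reader might conclude that every corrected set is a failure of music. The zero-effect run shows that up to 83% of slowly improving sets would be mislabelled that way.

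**Conclusion.** The point holds as a confounding and counting problem. Followed as written, the plan pools results before and after modelling and credits them to the music procedure, which affects all five research questions, most directly when only one of the two sets is corrected. This follows from the decision rule and does not rest on the simulation.

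Its size cannot be fixed from the documents. Modelling is likely to be common: about 74% to 99% of flat sets, and 2% to 90% of improving sets, depending on the reading of the stall rule and the assumed learning curve. How often a music procedure would be wrongly called effective depends on a modelling effect that the plan does not give. The gap should be closed before analysis.

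**What to change.** Leave the correction procedure unchanged and alter only how results are counted.

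1. Mark the first modelling session on each graph as the start of a separate music-plus-modelling phase. For questions 1 to 3, run the visual, split-middle, two-standard-deviation band and process-control analyses on the phase before modelling, and show the later phase separately.
2. Report three outcomes per set: acquired without correction; acquired with correction (contribution of music undetermined); discontinued. For sets acquired with correction, treat sessions to criterion for the music procedure as censored at modelling onset, and also report total sessions. Do not record these sets as a failure of music. Because stalling itself triggers the censoring, present these counts descriptively.
3. Flag the three-week retention score of any modelled set, and report the question 5 comparison with and without those sets.

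This needs about one paragraph across the Seventh Step and section 8, and no extra visits, since scores are already graphed by day; only the modelling start date must be recorded. The price is that fewer sets give an unconfounded music-alone result. A set corrected early may also have too few points for some rules, such as the seven-point run in the process-control criteria.

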1. Music with lyrics (songs) presented simultaneously with written lyrics will be effective for facilitating recovery of reading of phrase-level material for participants with aphasia.
2. Music with lyrics followed by presentation of the written lyrics will also be effective for facilitating recovery of reading of phrase-level material for participants with aphasia.
3. Simultaneous presentation will be more effective than priming with the music/lyrics for facilitating recovery of reading of phrase-level material for participants with aphasia.
4. Simultaneous presentation will be more efficient for facilitating recovery of reading of phrase-level material for participants with aphasia.
5. Simultaneous presentation will result in greater retention of the trained material.

4. **Study Design:** Give a description of the research design including use of placebo, randomization and an explanation of what is experimental. Include type of study: descriptive, retrospective, cross-sectional, longitudinal, prospective observational, pilot, experimental (controlled or non-controlled) or pilot.

This investigation uses a single-subject, adapted alternating research design to compare two different experimental conditions using music with lyrics combined with visual stimulation of the written lyrics, to extend the emotional word effect to phrases, in order to stimulate reading comprehension of the trained material for patients with aphasia. The two music conditions include 1) music with sung lyrics simultaneously with silent reading of the written lyrics; and 2) music with sung lyrics, followed by silent reading of the written lyrics (i.e. priming with the music). A control set without music will be used additionally within every third session to detect potential history and maturation effects. All conditions will be followed by a silent reading phrase-completion task composed of written words from the total combined sets of stimuli.

5. **Study Population:** Describe the subject population, including age, gender, ethnic characteristics and health status. State the inclusion/exclusion criteria along with how this was determined, and by whom. Please state whether pregnant women, children, or other vulnerable groups will be included or excluded. Provide rationale for using or excluding special populations. State the number of subjects or subject records necessary to complete the research.

Considerations in Participant Selection

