Research procedures for the study are described below. None of these procedures will be billed to the patient or third party insurers. When the patient is seen at CFMH Rehab or Roanoke Day Rehab, during the song testing, baseline, and intervention phases, the subject's normal speech therapy sessions will be cut from approximately 60 to 45 minutes. The research interventions will immediately follow. The research sessions will take, on average, an additional 45 minutes. When seen at CRCH Inpatient Rehab, the speech therapy sessions will not change other than reading. The Inpatient Rehab SLPs will receive the referral for ST and conduct an initial evaluation of patients for clinical purposes. This will include standard testing procedures for speech/language and swallowing. Patients with a diagnosis of left MCA CVA will be identified using the inclusion-exclusion checklist by the Inpatient Rehab SLPs who will then inform patients of the study and ask at a standard speech therapy session if the patient and legally authorized representative or person of the patient's choosing would agree to meet, via Carilion Secure Videoconferencing, with the Rehab Director to discuss the possibility of being in a research study. The treating SLP will notify the recruiter of the patient's decision. If the patient is recruited, the PI will be notified by the recruiter and the PI will schedule and conduct the Informed Consent interview. All research interventions will be scheduled after 2:30 pm and conducted by the PI onsite.

First Step--ST evaluation (standard procedure) and identification based on inclusion/exclusion criteria. (Expected length of time one visit).

Second Step—At CFMH Outpatient, Recruitment interview with Rehab Director. The treating SLP will inform the PI of new referrals. The PI will then check the EMR for preselection, and inform the recruiter of appropriate referrals to be contacted for recruitment. The Rehab Director will contact the potential participant to discuss the possibility of being in a research study. If the patient/representative agree, then a mutually agreeable time will be scheduled, probably before or after a standard therapy visit. The Rehab Director will notify the speech therapist researcher of the patient's decision on whether to further discuss participation in research.

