Sixth Step--Baseline phase, all 30 phrases (see attachment 1) will be tested using the phrase completion task (see attachment 2). Both correct responses and participation will be verbally reinforced. Results will be analyzed by the ST to ensure that the sets are of equal difficulty for each participant. (Expected length of time 5 visits or 2 weeks)

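### One BDAE reading test before and one after treatment cannot show generalization from the music; the change should be reported as descriptive only

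*Combined protocol and SAP*

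**What the plan says.** The Fourth and Eighth Steps in section 6 each give the BDAE-3 reading subtests at a single visit, before baseline and after intervention. Section 7 (Outcome Measures and Time Points) gives the purpose of the second test: "immediately following completion of intervention to assess generalization to non-trained stimuli".

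Section 6 also describes what else happens between the two tests:

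- At CFMH and Roanoke Day Rehab, during song testing, baseline and intervention, "normal speech therapy sessions will be cut from approximately 60 to 45 minutes". The research work follows directly: "The research sessions will take, on average, an additional 45 minutes".
- At the inpatient site: "When seen at CRCH Inpatient Rehab, the speech therapy sessions will not change other than reading". The exception for reading is not explained.
- In baseline (Sixth Step) all 30 phrases are tested without music. "Both correct responses and participation will be verbally reinforced".
- In the intervention phase (Seventh Step) the two music sets alternate from visit to visit. The phrase-completion task is then given, "including the ten phrases from the songs played that day and the five control phrases, without music".

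Section 4 states the safeguard against outside influences: "A control set without music will be used additionally within every third session to detect potential history and maturation effects".

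Section 5 sets no minimum time since stroke; section 7 lists time post onset among the characteristics to be reported. Section 8 gives no analysis for the BDAE. Its one mention of generalization concerns words in verbal expression and relies on comparing the control treatment with the two interventions.

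**The concern.** The BDAE is the plan's only reading test on untrained material. The Significance paragraph in section 2 looks forward to showing better therapy for language recovery, reading comprehension included. A reader who sees a BDAE gain under the stated purpose would naturally take it as transfer from the music treatment. Standard therapy, recovery after stroke, retesting, or reading practice without music could produce the same gain, and the plan has no measurement that would tell them apart. At stake is what the trial may say about reading beyond the trained phrases. The trained-phrase and retention comparisons, which answer the five research questions, are not in question here.

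**Working it through.** The plan states no effect size, variability, test or threshold for the BDAE, so there is no figure to reproduce. The check has two parts: whether any design feature separates the explanations, and how much time and therapy lie between the tests.

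**Part 1. What could separate the explanations**

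| Influence between the tests | Source | Feature that isolates it on the BDAE |
|---|---|---|
| Standard speech therapy | Section 6, Procedures | None; it continues at every site |
| Recovery | Section 5 sets no minimum time since stroke | None; time post onset is reported only |
| Retesting | Section 6, Fourth and Eighth Steps | None; one test on each side, no repeated baseline |
| Reinforced reading without music | Section 6, Sixth Step | None; it comes after the pretest |
| The other music condition | Section 6, Seventh Step | None; each participant receives both before the posttest |

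The control phrases are scored on the phrase-completion task only, so they yield no BDAE value. The comparison that section 8 describes for generalization needs separate data points for control and each intervention. The BDAE supplies one change per participant, so 4 to 10 changes in all (section 5). None comes from a participant without standard therapy or with only one music condition.

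**Part 2. Time and therapy between the tests**

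*Weeks.* Baseline 2 plus intervention 2 to 12 gives 4 to 14 weeks, song testing not counted. The spread of 14 − 4 = 10 weeks agrees with the stated overall duration, 20 − 10 = 10 weeks.

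*Visits, upper end.* The plan states: "Total number of visits: 16-48; total length of time 10-20 weeks per patient".

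- Removing consent, pretest, posttest and follow-up: 48 − 4 = 44.
- If the total also counts the evaluation and recruitment visits: 48 − 6 = 42.
- From the baseline rate of 5 visits in 2 weeks, or 2.5 per week: 12 × 2.5 = 30 intervention visits, plus 5 baseline and 2 song-testing visits, gives 37.

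The upper end is therefore 37 to 44, depending on how visits are counted.

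*Visits, lower end.* The same three counts give 16 − 4 = 12, 16 − 6 = 10, and (2 × 2.5) + 5 + 1 = 11. The last two are not attainable with five baseline visits. The mastery criterion needs three consecutive visits on each of two alternating sets, so at least 3 + 3 = 6 intervention visits. Stopping a set for lack of progress is no quicker, because it needs three visits without an increase and then a correction procedure. The floor is 1 song-testing + 5 baseline + 6 intervention = 12 visits.

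*Hours, at CFMH and Roanoke Day Rehab, one 45-minute standard session per research visit.*

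- Lower: 12 × 45 / 60 = 9 h.
- Upper: 44 × 45 / 60 = 33 h.

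These hours are all speech therapy. The reading share is not stated and may be small or large. Hours at the inpatient site cannot be derived.

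*Reading without music in baseline.* 5 visits × 30 phrases = 150 phrase readings, if all 30 are tested at each visit. These are study phrases, not BDAE items.

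**The case against.** The strongest reply is that the BDAE carries no formal conclusion. It is absent from the primary objective, the research questions, the hypotheses and the listed dependent variables, and section 8 gives it no test or decision rule. On that view it is already descriptive, and the stated purpose only explains why the test is given. This stands as far as importance goes and keeps the point below a major one. It does not remove the point: nowhere is the BDAE change called descriptive or its limits listed, so the stated purpose is all that guides a reader.

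A second reply is that the control phrases address history and maturation, and that each participant is his or her own control. Flat control phrases would make general recovery or therapy a less likely explanation, and that indirect evidence deserves mention when results are reported. But the own-control argument in section 5 concerns comparing two treatments. The BDAE has no counterpart to the control set.

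A third reply concerns the inpatient site, where the unexplained exception for reading may mean that reading is taken out of standard therapy. That could be a partial safeguard. The text does not say so, and the remaining therapy continues.

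A reader might also infer that the sponsor intends to report a BDAE gain as caused by the music. The documents contain no such statement; they give a purpose, not a reporting rule.

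**Conclusion.** The point holds as a minor-to-moderate correction to interpretation. A single before-and-after BDAE change cannot be credited to the music treatment or to either of its two forms. The 4 to 14 weeks follow from the stated durations. The 12 to about 44 visits and 9 to 33 hours rest on one standard session per research visit at CFMH and Roanoke Day Rehab, five baseline visits, and the visit count that gives the highest upper end.

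Two stronger readings are not supported. The hours are not a measure of competing reading therapy, because the reading content of standard sessions is unknown. Nor can a size be put on a spurious gain, because the documents give no BDAE scores or variability. The conclusion rests on the structure of the design, not on these figures.

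**What to change.** In section 7, replace the generalization purpose with wording such as: 'to describe change in reading of non-trained material; BDAE pre-post change will be reported per participant as descriptive only, beside time post onset, and will not be interpreted as generalization from the music treatment.' Time post onset is already collected, and section 8 allows other outcomes to be secondary and descriptive. The cost is one sentence by amendment and the loss of a claim that the design cannot support. No test, visit or decision rule is added.

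Optionally, log the minutes of reading work in standard therapy at each visit between the two tests, as one REDCap field with about 12 to 44 entries per participant. Where the PI is not the treating therapist, that therapist would have to pass the minutes on, because REDCap access is limited to the research team. The log gives context only. It does not remove the confounding, and 4 to 10 participants are too few for a credible adjustment.

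If the sponsor wants to keep a generalization claim, the BDAE would need something like repeated untrained-reading probes during baseline or a control language subtest not expected to change. That adds testing and is not proposed here.
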